3.2.5.3 Age at Entry Into Study

The adjusted age at entry into study is defined as the adjusted age at the screening date. This is also referred to as “Age at entry into study”

3.2.6 Body Mass Index

Body Mass Index (BMI) will be calculated using the formula:

$$\text{BMI} = \text{weight (kg)} / (\text{height (m)})^2.$$

3.2.7 Exposure to Study Medication

The date of first dose of study medication is defined as the first study medication dose date according to the First Administration CRF.

The date of last dose of study medication is defined as the last dose of study medication reported on the standard Trial Termination CRF.

The number of days of exposure is defined as the stop date minus the treatment start date +1 day. Days with unknown or zero dosing which occur prior to the last dose of study medication in the study will be included in the calculation.

3.3 Definition of Baseline Values

For by-visit analysis, baseline is defined as following:

For efficacy variables (except partial seizure frequency collected from DRC), safety variables, laboratory variables (blood chemistry, hematology), vital signs, and body weight, baseline is defined as the last value prior to the first dose of study medication (LEV).

In general: Change from Baseline (CfB) is calculated as:

$$\text{CfB} = \text{Post-Baseline value} - \text{Baseline value}.$$

If not noted otherwise, change from Baseline is calculated for post Baseline visits according to the visit schedule including unscheduled visits and for Last Visit.

For percent reduction in partial seizure frequency by DRC, a baseline value is calculated from retrospective baseline period + selection period.

For by-analysis visit, baseline is calculated from Analysis Visit Baseline value.

3.4 Protocol Deviations

After all CRFs have been retrieved and entered, all queries issued and answered to the extent possible, and prior to locking the database, a final Data Evaluation Meeting (DEM) will be held.

The meeting covers but is not limited to the following tasks:

- Review and assessment of important protocol deviations
- Agreement/confirmation of data handling rules
- Evaluation of statistical methodology

Important protocol deviations are to be classified into important for:

- Efficacy
- Conduct/Patient Management

Criteria and rules for the identification and classification of important protocol deviations regarding their impact on study conduct/subject handling and/or the assessment of efficacy are to be setup and to be minuted. Decisions made during the meeting are minuted.

3.5 Analysis Sets

The following sets are defined for this study:

- Enrolled Set (ES)
- Safety Sets:
 - SS_A (Safety Set [Adjunctive therapy])
 - SS_M (Safety Set [Monotherapy])
- Full Analysis Sets:
 - FAS_A (Full Analysis Set [Adjunctive therapy])
 - FAS_M (Full Analysis Set [Monotherapy])
- Pharmacokinetic Per-Protocol Set (PK-PPS)
 - PK-PPS_A [Pharmacokinetic-Per-Protocol Set (Adjunctive therapy)]
 - PK-PPS_M [Pharmacokinetic-Per-Protocol Set (Monotherapy)]

If not stated otherwise, presentation of:

- Disposition and important protocol deviations are based on the ES
- Demographics, other baseline characteristics, safety, and exposure data are based on the SS_A and SS_M
- Efficacy data are based on the FAS_A and FAS_M.

3.5.1 Enrolled Set

The Enrolled Set (ES) will consist of all subjects enrolled (which include all subjects screened) into the Selection Period.

3.5.2 Safety Set

The SS_A will include all enrolled subjects on adjunctive therapy who receive at least 1 dose of study medication in the Evaluation Period.

The SS_M will include all enrolled subjects on monotherapy who receive at least 1 dose of study medication in the Evaluation Period.

For subjects who were directly enrolled in the Second Period based on the protocol prior to Amendment 3, after re-mapping they will be considered as entering in the Evaluation Period if they receive at least 1 dose of study medication in the Dose Adjustment Period.

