2.3.1 Study Periods

- **Retrospective Baseline Period**

Seizure counts during the 2 weeks prior to Visit 1 will be used as a Retrospective Baseline Period.

- **First Period**

- Selection Period (maximum of 9 days)
- Evaluation Period (6 weeks)
- Down-Titration Period (up to 4 weeks)
- Safety Follow-Up Period (2 weeks)

- **Second Period**

- Maintenance Period (until approval or the program is discontinued)
- Down-Titration Period (up to 4 weeks)
- Safety Follow-Up Period (2 weeks)

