3.2.1.2.2 Subjects enrolled prior to Protocol Amendment 3 who are 48h video-EEG Failures

3.2.1.2.2.1 First period

Selection Period:

- Start: Day of Visit 1
- End:
 - Subject dose not discontinue from study: 1 day before Visit 6, or
 - Subject discontinues from study: “Date of last contact with Subject” on “Study Termination, Screen Failure Packet” CRF.

3.2.1.2.2.2 Second Period

For 48h video-EEG failures, the data will be re-mapped according to Table 3-2 and will be included in the efficacy and safety analysis.

Dose Adjustment Period (only if subject does not discontinue at Visit 2):

- Start: Day of Visit 6
- End: First of:
 - Day of Visit 9, or
 - Day of first Early Discontinuation Visit

1. For subjects who discontinued during the Dose Adjustment Period:

Down-Titration Period (only when subject is not on minimum dose):

- Start: 1 day after Day of End of Dose Adjustment Period
- End: Day of Last Early Discontinuation Visit; if Day of Last Early Discontinuation Visit is missing, the date of last dose of study medication will be used

Followed by

Safety Follow-Up Period (safety follow-up visit will take place when subject is 2 weeks off study drug, ie, on 0mg/kg dose):

- Start: 1 day after Day of Down-Titration Period or 1 day after Day of Dose Adjustment Period
- End: Day of Safety Follow-Up Visit

2. For subjects who did not discontinue during the Dose Adjustment Period:

Maintenance Period:

- Start: 1 day after Day of Visit 9
- End: First of:
 - Day of first Early Discontinuation Visit, or
 - Day of end of study*

* Day of end of study as determined by sponsor, connected to market approval or completion of development of LEV in subjects 1 month to <4 years

3. For subjects who discontinue from maintenance period:

Down-Titration Period (only when subject is not on minimum dose):

- Start: 1 day after Day of End of Maintenance Period
- End: Day of Last Early Discontinuation Visit; if Day of Last Early Discontinuation Visit is missing, the date of last dose of study medication will be used

Followed by

Safety Follow-Up Period (safety follow-up visit will take place when subject is 2 weeks off study drug, ie, on 0mg/kg dose):

- Start: 1 day after Day of End of Down-Titration Period or 1 day after Day of End of Maintenance Period
- End: Day of Safety Follow-Up Visit

4. For subjects who did not discontinue from Maintenance Period:

- The end date will be captured on “study termination” CRF.

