3.2.2 Schedule of Study Assessments

The study protocol gives the overall study schedule and the permissible intervals for these visits expressed as the number of days relative to Visit 3: Section 5.2 of protocol.

Subjects who were directly enrolled in the Second Period based on the protocol prior to Amendment 3 will also be included in the efficacy and safety analysis with remapping of visit numbers to correspond to the ones for subjects who enrolled in the First Period.

[Table 3–1](#) presents the assessment schedule for subjects:

- who are enrolled prior to Protocol Amendment 3 and are not 48h video-EEG failures; or
- who are enrolled according to Protocol Amendment 3; or
- who are enrolled prior to Protocol Amendment 3 and are 48h video-EEG failures

This document cannot be used to support any marketing application and any extensions or variations thereof.
PUBLIC COPY

Table 3–1: Assessment Schedule

Study Visit	Target day*	Visit Window	Week number
Subjects:			

 • who are enrolled prior to Protocol Amendment 3 and are not 48h video-EEG failures or • who are enrolled according to Protocol Amendment 3 			
Evaluation Period			
Visit 3	Day 1		Week 0
Visit 4	Day 15	Day 11 to Day 19	Week 2
Visit 5	Day 29	Day 25 to Day 33	Week 4
Visit 6	Day 43	Day 39 to Day 47	Week 6
Maintenance Period			
Visit 8	Day 71	Day 64 to Day 78	Week 10
Visit 10	Day 99	Day 92 to Day 106	Week 14
Visit 11	Day 127	Day 120 to Day 134	Week 18
Visit 12	Day 155	Day 148 to Day 162	Week 22
Visit 13	Day 183	Day 176 to Day 190	Week 26
Visit 15	Day 267	Day 260 to Day 274	Week 38
Visit 16	Day 351	Day 337 to Day 365	Week 50
Visit 17	Day 435	Day 421 to Day 449	Week 62
Every 12 weeks			
Subjects:			

 • who are enrolled prior to Protocol Amendment 3 and are 48h video-EEG failures 			
Dose Adjustment Period			
Visit 6	Day 1		Week 0
Visit 7	Day 15	Day 11 to Day 17	Week 2
Visit 8	Day 29	Day 25 to Day 33	Week 4
Visit 9	Day 43	Day 39 to Day 47	Week 6
Maintenance Period			
Visit 10	Day 57	Day 50 to Day 64	Week 8
Visit 11	Day 85	Day 78 to Day 92	Week 12
Visit 12	Day 113	Day 106 to Day 120	Week 16
Visit 13	Day 141	Day 134 to Day 148	Week 20
Visit 14	Day 183	Day 176 to Day 190	Week 26
Visit 15	Day 225	Day 221 to Day 232	Week 32
Visit 16	Day 309	Day 295 to Day 323	Week 44
Visit 17	Day 393	Day 379 to Day 407	Week 56
Every 12 weeks			

Table 3–1: Assessment Schedule

Study Visit	Target day*	Visit Window	Week number

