10.2.1.2 Assignment of AEs to Periods/Onset of AEs

An AE is assigned to that study period the subject is in during onset of the AE. For the definitions of study periods see [Section 2.3.1](#).

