10.2.2 Tables

Tables will be presented for subjects on adjunctive therapy and for subjects on monotherapy, separately.

AE Summaries

For the First Period all TEAE summaries will be presented for all age categories combined on the SS_A and SS_M.

For the combined First and Second Period all TEAE summaries will be presented for all age categories combined on the SS_A and SS_M.

The following summaries will be produced, for the First, and for the combined First and Second Periods):

- Number and percent of subjects with AEs – Overview.
Overview of the Incidence of AEs will include all subjects with at least one TEAE, serious TEAEs, subject discontinuations due to TEAEs, drug-related TEAEs, severe TEAEs, and all deaths (AEs leading to death).
- Incidence of AEs – Overview
- Number and percent of subjects with TEAEs, and Incidence of TEAEs
- Number and percent of subjects with serious TEAEs, and Incidence of serious TEAEs
- Number and percent of subjects with TEAEs by relationship to study medication, and Incidence of TEAEs by relationship to study medication
- Number and percent of subjects with serious TEAEs by relationship to study medication, and Incidence of serious TEAEs by relationship to study medication
- Number and percent of subjects with serious drug-related TEAE
- Number and percent of subjects with TEAEs by Intensity, and Incidence of TEAEs by Intensity
- Number and percent of subjects with serious TEAEs occurring in at least 5% of the subjects, and Incidence of serious TEAEs occurring in at least 5% of the subjects
- Number and percent of subjects with TEAEs leading to (permanent) discontinuation of study medication

Note: permanent discontinuation: when in the Adverse Event CRF the item “Action taken with study Medication” is answered with “Drug Permanently Withdrawn”. And Incidence of TEAEs leading to (permanent) discontinuation of study medication

AEs will be summarized by MedDRA SOC and MedDRA PT. The number and percentage of subjects experiencing each event at least once will be summarized.

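### The SAP does not say whether TEAEs in the Dose Adjustment Period of the directly enrolled video-EEG failures are First Period events; on the dated period definitions they are not, and First Period incidence would be understated

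*SAP*

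**What the plan says.** Five places in the SAP bear on this.

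- **Set membership (3.5.2).** Of subjects enrolled directly into the Second Period before Amendment 3 it says: "after re-mapping they will be considered as entering in the Evaluation Period". The condition is one or more doses taken during Dose Adjustment. They therefore belong to SS_A or SS_M.
- **Tables (10.2.2).** "For the First Period all TEAE summaries will be presented for all age categories combined on the SS_A and SS_M". There is no separate First Period safety set.
- **AE rule (10.2.1.2).** "An AE is assigned to that study period the subject is in during onset of the AE". For the period definitions it refers to Section 2.3.1.
- **Period list (2.3.1).** The Evaluation Period is in the First Period. The Second Period list opens with "Maintenance Period (until approval or the program is discontinued". A Dose Adjustment Period appears nowhere in the list.
- **Dated periods for video-EEG failures (3.2.1.2.2).** Their First Period contains only Selection, which ends the day before Visit 6. The entry that begins "Dose Adjustment Period (only if subject does not discontinue at Visit 2" stands under the Second Period heading. It runs from Visit 6 to the earlier of Visit 9 and the first Early Discontinuation Visit.

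The same Second Period subsection also says: "For 48h video-EEG failures, the data will be re-mapped according to Table 3-2 and will be included in the efficacy and safety analysis".

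**The concern.** The First Period numerator and denominator come from different rules. The denominator follows set membership, where these subjects are treated as having entered the Evaluation Period. The numerator follows the period at AE onset, where their early weeks on drug carry a different label. Nothing in the SAP ties the two together.

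First Period incidences of TEAEs, of serious events and of TEAEs leading to discontinuation are secondary safety variables (SAP 2.2.3.2; Protocol 4.3.2.1). Any mismatch of this kind pushes them down, never up, and the events left out are those of the titration weeks. The study has a single arm, so no control group carries the same error.

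**Working it through.** The documents give neither a TEAE incidence nor the number of video-EEG failures, so there is no stated figure to reproduce. The check is a trace of the rules followed by an illustration.

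**1. Denominator.** By SAP 3.5.2 one dose in Dose Adjustment puts the subject in SS_A or SS_M, and by 10.2.2 the First Period tables use those sets. An explicit rule that limits a by-period denominator to subjects who entered the period is given for laboratory data (10.3.1), vital signs (10.4.1.1) and weight (10.4.3.1). It is not given for AEs.

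**2. Numerator.** Visit 6 is Day 1 for these subjects (Table 3-1), and their Selection Period ends the day before. A TEAE starts or worsens on or after first dose (10.2.1), and a worsening is recorded as a new AE entry (4.2.3). So none of their TEAEs can have onset in Selection, the only period listed under their First Period. Visit 9 has target Day 43 and window "Day 39 to Day 47", so about six weeks on drug fall under the Second Period heading.

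**3. Whether the re-mapping closes the gap.** Table 3-2 aligns Visits 6, 7, 8 and 9 of these subjects with Visits 3, 4, 5 and 6 of the others. It maps visits under one merged period header. It sets no boundary between First and Second Period and maps no AE onset dates. SAP 2.3.1 contains no start or end dates, and SAP 5.1.1.4 sends the reader to 3.2.1.2 for when a period starts and ends. For the primary efficacy variable, SAP 8.1.1 says expressly that the analysis visit is used so that these subjects can be included. There is no matching sentence for AEs.

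**4. Arithmetic.** Let N be the size of the set, m the number of video-EEG failures in it, and p_n and p_f the six-week TEAE incidence in non-failures and failures.

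- Dated definitions: incidence = (N − m) × p_n / N
- Dose Adjustment counted as Evaluation: incidence = [(N − m) × p_n + m × p_f] / N
- With p_n = p_f = p, the ratio of the first to the second is (N − m)/N, and the loss in percentage points is p × m/N.

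Assumptions: N = 38 (the planned number for the primary analysis), m from 1 to 10, p of 40%, 60% or 80%, equal in both groups.

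| m of 38 | Factor (38 − m)/38 | Reported if p = 60% | Loss, p = 40% | Loss, p = 60% | Loss, p = 80% |
|---|---|---|---|---|---|
| 1 | 37/38 = 0.974 | 58.4% | 1.1 | 1.6 | 2.1 |
| 3 | 35/38 = 0.921 | 55.3% | 3.2 | 4.7 | 6.3 |
| 5 | 33/38 = 0.868 | 52.1% | 5.3 | 7.9 | 10.5 |
| 10 | 28/38 = 0.737 | 44.2% | 10.5 | 15.8 | 21.1 |

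For the 10 planned monotherapy subjects, m = 1 gives 9/10 = 0.9 (60% reported as 54.0%) and m = 3 gives 7/10 = 0.7 (42.0%).

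**5. Exposure and compliance.** In SAP 7.1, First Period compliance is based on the duration of the Evaluation Period and Second Period compliance on that of the Maintenance Period. Dose Adjustment falls in neither. SAP 10.1.1 sets per-period exposure equal to period duration, so it inherits the same gap.

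**The case against.** The best case on the other side is that the SAP, read as a whole, already treats Dose Adjustment as Evaluation. SAP 3.5.2 makes dosing in Dose Adjustment the trigger for entering the Evaluation Period. The AE rule cites 2.3.1, not 3.2.1.2.2.2, and 2.3.1 places Evaluation in the First Period. The re-mapping sentence speaks of the data in general and names the safety analysis. Protocol 13.2 intends these subjects to correspond to those enrolled in the First Period. On that reading the factor is 1.0.

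There are two further points. The general denominator rule (SAP 3.1.1) is flexible, and the AE section does not say in terms that the whole set is the divisor. And no event disappears: the combined-period tables count it, and the AE listing shows period and relative day.

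Much of this stands. A reader might infer that First Period TEAE incidence is diluted as a matter of fact. The documents do not support that, because one plausible reading gives no dilution and m is unknown.

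What does not stand is the claim that the text settles the matter. The sentence in 3.5.2 is a rule for set membership and gives no period dates. Protocol 13.2 speaks of remapping visit numbers. SAP 8.3.2 still lists Evaluation and Dose Adjustment as separate periods when it defines seizure freedom.

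**Conclusion.** This is an unresolved conflict among SAP 2.3.1, 3.2.1.2.2.2, 3.5.2 and 10.2.1.2, not a demonstrated bias. If the tables are programmed from the dated period definitions with the full Safety Set as divisor, First Period incidence of TEAEs, serious TEAEs and TEAEs leading to discontinuation is multiplied by (N − m)/N. In the illustration the loss runs from 1.1 to 21.1 percentage points. If 3.5.2 governs, or if m = 0, there is no loss. The size rests on assumed values of m and p, on N = 38 and on equal rates in the two groups. Combined First and Second Period incidence does not change. The conflict should be resolved because two defensible readings of one plan give different values for secondary safety variables and no sentence chooses between them.

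**What to change.** State in SAP 2.3.1, 3.2.1.2.2.2 and 10.2.1.2 that, for subjects directly enrolled before Amendment 3, the Dose Adjustment Period (Visit 6 to the first of Visit 9 or the first Early Discontinuation Visit) is treated as the Evaluation Period, and so as First Period, for AE assignment. Section 2.3.1 must be among the places changed, because it is the one the AE rule cites. Apply the same rule to per-period exposure and compliance in 10.1.1 and 7.1. It would also help to report m beside the First Period tables.

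The cost is a short SAP clarification, with no new data and no change to conduct. The SAP Introduction allows revisions before the snapshot for the NDA submission. Compared with programming from the dated definitions, reported First Period incidence may rise.

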3.5.3 Full Analysis Set

The FAS_A will consist of all subjects in the SS_A who have at least 1 post-baseline efficacy assessment.

The FAS_M will consist of all subjects in the SS_M who have at least 1 post-baseline efficacy assessment.

3.5.4 Per Protocol Set

Not applicable.

3.5.5 Other analysis sets

The PK-PPS_A will consist of all subjects in the SS_A for whom at least 1 valid LEV plasma concentration-time record and dosing information are available.

The PK-PPS_M will consist of all subjects in the SS_M for whom at least 1 valid LEV plasma concentration-time record and dosing information are available.

3.6 Treatment Assignment and Treatment Groups

This is an open-label study with a single treatment arm; hence subjects will not be randomized.

3.7 Center pooling strategy

No pooling of centers is planned for this study.

3.8 Coding dictionaries

Medical history and adverse events (AEs) will be coded using the Medical Dictionary for Regulatory Activities (MedDRA) version 23.0 that is released for execution at UCB/Designee. Medication including anti-epileptic drugs (AEDs) will be coded using the World Health Organization Drug Dictionary (WHO-DD) WHO-DD SEP/2017 that is released for execution at UCB/designee. The applied version of the dictionaries will be explicitly mentioned in the respective tables and listings.

3.9 Changes to protocol-defined analyses

Not applicable.

3.10 Consideration for COVID-19

Since the target population of this study is infants or young children in which the population is not considered will be impacted on the efficacy and safety evaluation due to COVID-19. No additional amendment to CRF or analyses is required.

4 STATISTICAL ANALYTICAL ISSUES

4.1 Adjustments for Covariates

This section is not applicable for this study.

4.2 Handling of Dropouts or Missing Data

Days with missing seizure data will not be used for the calculation of seizure frequency per week. If subjects drop out, their seizure counts over the available period will be used and transformed into seizure frequency per week, by dividing the number of seizures during the available period by the number of days of that period, multiplied by 7.

Safety variables will be analyzed insofar as they are available, without imputation or carrying values forward.

Imputations for missing or partial values for dates for AEs and concomitant medications will be applied to determine if an event is to be considered treatment-emergent or concomitant. Across safety and PK analyses, only reported data will be used.

4.2.1 General Imputation Rule for Incomplete Dates

Where necessary for the calculation of derived variables, partial dates will be completed using the earliest calendar date based on the partial date provided. This rule is valid for all partial dates with the exception of the following:

- Start and stop dates of concomitant medication, [Section 4.2.2](#)
- Start and stop dates of Adverse Events, [Section 4.2.3](#)

Completely missing dates will not be replaced and the corresponding derived variables will be set to missing.

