6.6.1 Definitions and Derivations

6.6.1.1 Epilepsy Duration and Age at Onset

Date of first onset of epilepsy is documented in the Diagnosis of Epilepsy CRF. Based on this date, the duration of epilepsy and the age at onset is derived as follows:

- Epilepsy duration [months] = (date of Visit 1 – date of first seizure) / 30.4375
- Age at onset of epilepsy [months] = (date of first seizure – date of birth) / 30.4375.

6.6.1.2 Historical partial onset seizures and seizures of subtypes IA, IB, and IC during 2 weeks prior to Visit 1

The information if a subject experienced any seizures (note: this includes seizures other than partial onset seizures) is captured in the Historical Seizure Count CRF.

A subject is regarded as having experienced any simple partial seizures (subtype IA) during the past 2 weeks to Visit 1, if the number of simple partial seizures in the Historical Seizure Count is >0 for the past 2 weeks prior to Visit 1, otherwise the subject is regarded as not having experienced simple partial seizures during the past 2 weeks prior to Visit 1.

Analogously, this is done for:

- Experiencing complex partial seizures (subtype IB) during the past 2 weeks prior to Visit 1
- Experiencing partial evolving to secondarily generalized seizures (subtype IC) during the past 2 weeks prior to Visit 1
- Experiencing Generalized seizures (subtype II) during the past 2 weeks prior to Visit 1
- Experiencing unclassified epileptic seizures (subtype III) during the past 2 weeks prior to Visit 1.

6.6.1.3 Historical Partial Onset Seizures (Type I) During 2 Weeks Prior to Visit 1

A subject is regarded as having experienced any partial onset seizures (any subtype) during the past 2 weeks prior to Visit 1, if they experienced any simple partial seizures (subtype IA), complex partial seizures (subtype IB) or partial evolving to secondarily generalized seizures (subtype IC) during the past 2 weeks prior to Visit 1, otherwise they are not regarded as having had any partial onset seizures during the past 2 weeks prior to Visit 1.

6.6.1.4 Historical Seizure Count for Partial Onset Seizures During 2 Weeks Prior to Visit 1

The information regarding ILAE historical seizure count is captured on the “ILAE Seizure Classification History” CRF.

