6.6.2 Tables

A table Diagnosis of Epilepsy presents for subjects on adjunctive therapy and for subjects on monotherapy, separately:

- Summary statistics for age (months) at onset of epilepsy
- Summary statistics for duration (months) of epilepsy at study entry

A table ILAE Seizure Classification History presents a frequency distribution (number and percentage of subjects) for:

- Partial onset seizures (I), Total and in ILAE sub-classes as specified in the CRF (seizure description and ILAE seizure code) (eg, Simple partial (IA), Complex partial (IB), ...)
- Generalized seizures (II), Total and in ILAE sub-classes
- Unclassified epileptic seizures (III)

A subject can appear in more than 1 category.

A table Historical Seizure Count, Number and Percentage of Subjects presents for subjects on adjunctive therapy and for subjects on monotherapy, separately:

- Frequency distribution (number and percentage of subjects) for experiencing any seizure during the 2 weeks prior to Visit 1
- Frequency distribution (number and percentage of subjects) for experiencing any partial onset seizures
- Frequency distribution (number and percentage of subjects) for experiencing partial onset seizure subtypes (simple partial, complex partial, partial evolving to secondarily generalized)
- Frequency distribution (number and percentage of subjects) for experiencing any generalized seizures
- Frequency distribution (number and percentage of subjects) for experiencing any unclassified epileptic seizures

A table Historical Seizure Count, Descriptive Statistics presents for subjects on adjunctive therapy and for subjects on monotherapy, separately:

- Summary statistics for the number of any seizures during the 2 weeks prior to Visit 1

- Summary statistics for the number of partial onset seizures
- Summary statistics for the number of partial onset seizure subtypes (simple partial, complex partial, partial evolving to secondarily generalized)
- Summary statistics for the number of generalized seizures
- Summary statistics for the number of unclassified epileptic seizures

A table Classifications of Epileptic Syndromes presents for subjects on adjunctive therapy and for subjects on monotherapy, separately, a frequency distribution (number and percentage of subjects) for:

- Localization related classifications (with subdivisions)
- Generalized classifications (with subdivisions)
- Epilepsies and syndromes undetermined (with subdivisions)
- Special syndromes

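### The earliest-date rule for partial dates has no floor at birth, so a first-seizure date with the day missing can give a negative age at onset and an epilepsy duration longer than the child's life

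*SAP*

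**What the plan says.** SAP 4.2.1 sets the general rule. Where a derived variable needs it, "partial dates will be completed using the earliest calendar date based on the partial date provided". On scope it adds: "This rule is valid for all partial dates with the exception of the following", and lists only start and stop dates of concomitant medication and of adverse events. A separate sentence deals with dates that are wholly absent: "Completely missing dates will not be replaced and the corresponding derived variables will be set to missing".

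SAP 6.6.1.1 gives the source of the onset date, "Date of first onset of epilepsy is documented in the Diagnosis of Epilepsy CRF", and the two derivations: "Age at onset of epilepsy [months] = (date of first seizure – date of birth) / 30.4375" and "Epilepsy duration [months] = (date of Visit 1 – date of first seizure) / 30.4375".

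SAP 6.6.2 puts both results in the Diagnosis of Epilepsy table, separately for adjunctive therapy and monotherapy: "Summary statistics for age (months) at onset of epilepsy" and "Summary statistics for duration (months) of epilepsy at study entry". Under SAP 3.1.2 those statistics include the mean, median, quartiles, minimum and maximum. The listing in SAP 6.6.3 repeats duration and shows an age at first diagnosis.

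**The concern.** The first-seizure date is neither a medication date nor an adverse-event date, so the earliest-date rule governs it. The earliest date in a recorded month is the 1st, and for a child whose epilepsy began in the month of birth the 1st will usually precede birth. The 6.6.1.1 formulas then return a negative age at onset and a duration longer than the child has lived. Neither section limits the imputed date or says what to do with a negative result.

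The case is foreseeable here. Subjects are aged 1 month to under 4 years (protocol 6.1), and exclusion criterion 6 allows for status epilepticus in the first 10 days of life (protocol 6.2). Elsewhere the SAP does limit its imputed dates: SAP 8.3.2 moves an imputed diary-row date forward if it falls before the documented month or year. The missing floor at birth therefore looks like an oversight. At stake is whether a baseline table contains values that cannot be true; a single negative age would be its reported minimum.

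**Working it through.** The plan states no figure on this point, so there is none to reproduce. The check applies its own rule and formulas.

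**Inputs.** Imputation rule: SAP 4.2.1 (1st of the month if the day is missing; 1 January if month and day are missing). Formulas and divisor 30.4375: SAP 6.6.1.1. Calendar dates in the examples are assumed, and the date of birth is taken as complete.

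**1. Day missing, onset in the birth month.** Born 20 March 2020, true onset 28 March 2020 recorded as March 2020, Visit 1 on 20 June 2020. Imputed onset is 1 March 2020.
- Age at onset: -19/30.4375 = -0.62 months (true 8/30.4375 = 0.26).
- Duration: 111/30.4375 = 3.65 months (true 84/30.4375 = 2.76).
- Life at Visit 1: 92/30.4375 = 3.02 months. Duration exceeds it by 0.62, allowing for rounding: the same 19 days.

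**2. Month and day missing, onset in the birth year (hypothetical).** Born 15 September 2020, true onset 10 November 2020 recorded as 2020, Visit 1 on 15 December 2020. Imputed onset is 1 January 2020.
- Age at onset: -258/30.4375 = -8.48 months (true 56/30.4375 = 1.84).
- Duration: 349/30.4375 = 11.47 months (true 35/30.4375 = 1.15), against a life of 91/30.4375 = 2.99.

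**3. Day missing, onset in a later month than birth.** Born 20 March 2020, true onset 10 May 2020 recorded as May 2020. Imputed onset is 1 May, and age at onset is 42/30.4375 = 1.38 months (true 1.68). It is a little early, but not impossible.

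**4. All birth dates in a non-leap year, for records already of the affected type.**

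| Record | Negative age | Mean derived age | Minimum |
|---|---|---|---|
| Day missing, onset in birth month | 353/365 = 96.7% | -0.48 | -0.99 |
| Month and day missing, onset in birth year | 364/365 = 99.7% | -5.98 | -11.96 |

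The exceptions are births on the 1st of a month, or on 1 January, which give exactly 0.

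**5. Average error per affected record.** A simulation of 400,000 records took birth as uniform over the month or year and onset as uniform from birth to the end of it.
- Month-only: true mean 0.24, derived mean -0.48, so 0.24 + 0.48 = 0.72 months too early.
- Year-only: true mean 3.00, derived mean -5.97, so 3.00 + 5.97 = 8.97 months too early.

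The error in duration is equal and opposite.

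**6. Effect on a table mean.** Taking the planned numbers (38 adjunctive, 10 monotherapy), one month-only record moves the mean by 0.72/38 = 0.02 or 0.72/10 = 0.07 months. One year-only record would move it by 8.97/38 = 0.24 or 8.97/10 = 0.90 months.

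**The case against.** The strongest objection is that the trigger is not shown. The documents say only that the onset date is recorded on the Diagnosis of Epilepsy form; they do not say that the form accepts partial dates. If every onset date is complete, nothing happens. That stands, and it makes the point conditional.

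A reader might look to SAP 6.7.1, where medical-history dates are recorded by month and year only, as evidence that onset dates are partial. It does not serve: that text concerns the Medical History form, says that no imputation is foreseen, and feeds tables that exclude epilepsy. For the same reason it does not exempt the epilepsy-onset date from 4.2.1.

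The year-only figures are also open to challenge. They assume that the month of first seizure is unknown in a child under 4, and no text suggests that. They are kept as hypothetical. The 96.7% and 99.7% are simply the shares of birth dates that do not fall on the 1st of a month or on 1 January; they are not shares of trial subjects.

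Finally, there are general safeguards: computerised and manual data checks (protocol 12.3.2) and a Data Evaluation Meeting that confirms data-handling rules (SAP 3.4). A negative age should be noticed. These steps lower the chance that it reaches the report, but they supply no rule for what to put in its place.

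**Conclusion.** The point holds as a minor defect. As written, the SAP yields an impossible value when the day of first seizure is missing and onset is in the birth month, unless birth was on the 1st. The same would follow if month and day were both missing and onset was in the birth year, unless birth was on 1 January. The size is about 0.7 months per month-only record and, hypothetically, about 9 months per year-only record. Both averages rest on uniform birth and onset dates and on a complete date of birth. How many records are affected cannot be told from the documents.

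Three stronger readings are tempting and unsupported.

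- A reader might infer that the comparison with historical control is weakened. That comparison is a fixed 15% threshold on the median percent reduction (SAP 8.1.1) with no covariate adjustment (SAP 4.1). Age at onset and duration enter no test, endpoint or analysis set.
- A reader might infer that the errors fall mostly in the youngest age group. No calculation here involves age at entry, and SAP 6.6.2 does not ask for this table by age category.
- A reader might infer that any onset in the birth year gives a negative age. With the month recorded and later than the birth month, it does not (step 3).

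**What to change.** Add one sentence to SAP 4.2.1 or 6.6.1.1: a partial date of first seizure is imputed as the later of (a) the earliest calendar date consistent with the partial date and (b) the date of birth.

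Recomputed with this floor, the first example gives age at onset 0.00 and duration 3.02 months, equal to life at Visit 1; the second gives 0.00 and 2.99. The third example stays at 1.38 months, because its imputed date already falls after birth.

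The floor removes impossible values but not all bias: affected month-only records are set to 0 against a true mean of about 0.24 months (about 3.0 for hypothetical year-only records). Imputing the midpoint of the interval bounded by birth and Visit 1 would reduce that further, but it is optional.

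The cost is one sentence and one line of code. SAP section 1 allows revisions before the database snapshot for the NDA submission.
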